# **10.1.5 Storage**

Store between 2°-8°C. Do not freeze.

#### 10.1.6 Stability

The administration of ascorbic acid infusion must be completed within 72 hours of preparation. If not used immediately, the infusion solution must be refrigerated while also protected from light to keep the product stable. The maximum 72-hour period under refrigeration and protected light conditions includes the product administration period.

#### **10.1.7 Route of Administration**

Ascorbic acid should be administered by intravenous infusion. For intravenous injection, dilution into a large volume parenteral of water is recommended to minimize the adverse reactions associated with intravenous injection. Infusion will be administered at 0.75-1 gram per minute not to exceed 500 mL per hour. Ports are recommended but not mandatory due to frequency of infusion.

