# 1.0 SCHEMA

Total Number of Patients: 15

Olaparib is taken 300 mg BID orally

Ascorbate is given 1 g/kg, 2 times per week intravenously (first three doses [over 1.5 weeks]: titrate 0.25 g/kg, 0.5 g/kg, and 0.75 g/kg. Starting with cycle 1 week 2, the dose of Ascorbate will be 1 g/kg as long as this dose is tolerated)

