# 7.1 Study Calendar

Required Studies	Pre-study 	1 cycle = 28 days		EOT 	LONG TERM FU 			
	Screening	C1D1 	C1D8	C1D15 	C1D22 	CnDn 		
Visit Windows (days) 	-28	+/-3	+/-3	+/- 3	+/-3	+/- 3	-28	+/-28
TREATMENT								
Olaparib		X	X	X	X	X		
Ascorbic acid 		X	X	X	X	X		
ELIGIBILITY								
Inclusion/exclusion review	X							
HRR status 	X							
Informed consent	X							
ECG	X							
PHYSICAL								
Medical and Cancer History	X							
Physical Exam, Weight and ECOG 	X	X	X	X	X	X	X	X
Vital Signs 	X	X	X	X	X	X	X	X
AE/Toxicity Notation 		X	X	X	X	X	X	X
Concurrent meds 	X	X	X	X	X	X	X	X
LABORATORY								
Chemistry 	X	X	X	X	X	$X^7$	X	X
Hematology 	X	X				$X^7$	X	X
Urinalysis	X							
INR and PT/APTT 	X							
Urine Creatinine 	X 	X 				X 	X 	
Testosterone	X							
PSA 	X	X				$X^7$	X	X
G6PD 	X							
CORRELATIVE								
Blood Samples 	NA	X 				X 	$X^{10}$	
Urine Samples 	NA	$X^{11}$				$X^{11}$	$X^{11}$	
Optional Biopsy (Encouraged)	X 	N/A				X 		
DISEASE ASSESSMENT								
Radiologic Evaluation/ RECIST 1.1  or PCWG2	X 					X 	X 	
LONG TERM FOLLOW-UP 								X 

- Longer delays to be approved by the study sponsor. IRB approval is required for all eligibility waivers prior to enrollment. The window for the baseline Radiologic Evaluation/RECIST 1.1 is 6 weeks prior to C1D1.
- Each treatment cycle is 4 weeks (28 days). Ascorbic Acid dosing must be 2 times per week except week 1 when Olaparib is giving alone. The first infusion must occur on day 1 of each cycle and the second infusion can occur any other day during the week as long as it is at least 24 hours from the prior infusion.
- Ports are recommended but not mandatory due to the frequency of infusion.
- 4 After screening, physical exams may be limited as indicated by symptoms. ECOG Eastern Cooperative Oncology Group performance status. Physical exam (including vital signs and weight), ECOG status, AE/Toxicity notation and concurrent medication review have a -3 day window of day 1 of the cycle.

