**Table 2: Regimen Description** 

Regimen Description				
Agent	Dose	Route	Schedule	Cycle Length
Olaparib 	300 mg	Oral	Twice daily, days 1-28	28 days (4 weeks)
Ascorbic Acid	1 g/kg 	0.75-1 gram per minute IV 	Twice weekly  First dose on day 1 of the cycle	

- 1. Olaparib: two 150 mg tablets orally, with or without food, twice daily. The tablets are to be swallowed whole (do not chew, dissolve, or open the tablets). Administration should be in accordance with the package insert. $^{34}$
- 2. For a subject weighing 75 kg, the goal dose is 75 grams (1 g/kg), and the titrated dose schedule is  $18.75 \, \text{g}$ ,  $37.5 \, \text{g}$ , and  $56.25 \, \text{g}$  for cycle 1 only. Rounding the calculated doses to 19 g, 38 g, and  $56 \, \text{g}$  is acceptable. Subsequent doses would be 75 g. The maximum allowed dose for patients weighing over  $100 \, \text{kg}$  is  $100 \, \text{g}$ .
- 3. Infusion time is approximate (± 15 minutes) and may need to be adjusted based on patient tolerability. Infusion time is estimated to be between 90-120 minutes.
- 4. The ideal schedule for ascorbic acid is 3-4 days apart for administration. However, ascorbic acid can be safely administered on consecutive days (at least 24 hours apart). The day that ascorbic acid can be administered can be shifted in the event of holidays, inclement weather, and other reasons for clinic closure to even three consecutive days.

Subsequent ascorbic acid infusions may not be given less than 24 hours apart.

Acute reactions will be managed using standard therapy for acute drug reactions as per institutional standard of care.

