# 7.6.2 Ascorbic Acid Administration

For the first cycle, on cycle 1 day 8, collect blood for CTCs and then start Ascorbic Acid. The first three doses of ascorbic acid will be titrated as such: 0.25~g/kg, 0.5~g/kg, 0.75~g/kg in 1000ml of sterile water (not to exceed 500 mL per hour). If tolerated, the subsequent doses will be 1 g/kg. Infusions will be twice a week, and should not be less than 24 hours apart. It is recommended that ascorbic acid be given through a port due to frequency of infusion, but a port is not required.

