8.2.2.2 Olaparib Dose Modifications for concurrent Renal Impairment

If subsequent to study entry and while still on study therapy, a patient's estimated CrCl falls below the threshold for study inclusion ( $\geq$ 51 mL/min), retesting should be performed promptly.

For patients who develop moderate renal impairment (CrCl < 50 mL/min), hold dose until recovery.

Olaparib has not been studied in patients with severe renal impairment (creatinine clearance  $\leq$ 30 mL/min) or end-stage renal disease; if patients develop severe impairment or end stage disease, it is recommended that olaparib be discontinued.

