# **Renal Impairment**

If subsequent to study entry and while still on study therapy, a patient's estimated CrCl falls below the threshold for study inclusion ( $\geq$ 51 ml/min), retesting should be performed promptly.

A dose reduction is recommended for patients who develop moderate renal impairment (calculated creatinine clearance by Cockcroft-Gault equation or based on a 24 hour urine test of between 31 and 50 ml/min) for any reason during the course of the study: the dose of olaparib should be reduced to 200 mg twice daily.

Because the CrCl determination is only an estimate of renal function, in instances where the CrCl falls to between 31 and 50 mL/min, the investigator should use his or her discretion in determining whether a dose change or discontinuation of therapy is warranted.

Olaparib has not been studied in patients with severe renal impairment (creatinine clearance  $\leq 30$  ml/min) or end-stage renal disease; if patients develop severe impairment or end stage disease it is recommended that olaparib be discontinued.

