# 10.1.4 Preparation

When dispensing vials, use aseptic technique. Dispense entire contents in aliquots under a laminar flow hood without delay. Prepare stoppers with a suitable antiseptic technique. Do not use unless solution is clear and seal is intact. Parenteral drug products should be inspected visually for particulate matter and discoloration prior to administration, whenever the solution and container permit. Ascorbic acid should be diluted in sterile water for injection (final volume of 1000ml).

The ascorbic acid for infusions will be prepared by the pharmacy. The calculated dose of ascorbic acid will be diluted in Sterile Water for injection USP.

A study-specific worksheet will be completed when preparing ascorbic acid infusions. The worksheet will document the dose prepared and calculations for dose preparation.

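### The dosing instructions contradict each other on ascorbate start day, ascorbate infusion rate, and olaparib handling in moderate renal impairment and with unavoidable CYP3A inhibitors

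*Combined protocol and SAP*

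**What the plan says.** **Infusion rate.** Section 10.1.7 sets a mass rate and a volume cap together: "Infusion will be administered at 0.75-1 gram per minute not to exceed 500 mL per hour". Section 10.1.4 fixes the volume: "Ascorbic acid should be diluted in sterile water for injection (final volume of 1000ml"). Section 7.6.2 repeats the 1000 mL volume and the cap. Note 3 to Table 2 adds: "Infusion time is estimated to be between 90-120 minutes", and calls the time approximate (± 15 minutes) and adjustable for tolerability.

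**Ascorbate start.** Section 7.6.2: "For the first cycle, on cycle 1 day 8, collect blood for CTCs and then start Ascorbic Acid". Footnote 2 to the study calendar (Section 7.1) also has olaparib given alone in week 1. Its next sentence reads "The first infusion must occur on day 1 of each cycle", with no exception for cycle 1. The calendar grid marks ascorbic acid at C1D1, and Table 2 puts the first dose on day 1. The schema (Section 1.0) has three titration doses over 1.5 weeks, then: "Starting with cycle 1 week 2, the dose of Ascorbate will be 1 g/kg as long as this dose is tolerated".

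**Moderate renal impairment.** Section 8.2.2.2: "For patients who develop moderate renal impairment (CrCl < 50 mL/min), hold dose until recovery". Table 5 gives a reduction at a creatinine clearance of 31–50 mL/min. The Renal Impairment subsection under 8.2.2.3 recommends the same: "the dose of olaparib should be reduced to 200 mg twice daily". It then leaves the choice between changing the dose and stopping to the investigator.

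**Unavoidable CYP3A inhibitor.** Section 8.2.2.1 takes the patient off protocol treatment. Section 7.7 and Table 6 keep the patient on a reduced olaparib dose (150 mg twice daily for a moderate inhibitor, 100 mg for a strong one). Section 7.7 allows the dose to go back up after washout; Section 8.2.2.3 forbids any escalation after a reduction.

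**The concern.** These are different instructions for the same patient in a multi-center trial of a combination that Section 4.2.8 says has no clinical data in this disease. Depending on the section a site follows, the patient is infused at a different speed, titrated on different days, and held, reduced or taken off treatment.

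Four consequences reach the data:

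- **Analysis sets.** Sections 12.4 and 13.7 require at least one dose of both agents for the safety set and for primary-endpoint evaluability. A patient who stops in week 1 is in both sets under a day 1 start and in neither under a day 8 start. Section 13.5 decides on 2 or more responses in 12 patients, so one patient can matter.
- **Drop-outs.** The CYP3A conflict directly determines who leaves treatment. The renal conflict can, because Section 8.2.2.3 ends all study therapy after an olaparib interruption of more than 4 weeks for toxicity.
- **Correlative samples.** Section 11.2 labels both C1D1 and C1D8 as pre-infusion. The C1D8 γH2AX sample reflects olaparib alone if ascorbate starts on day 8, but follows earlier ascorbate doses if it starts on day 1.
- **Safety reporting.** Section 7.10 treats dosing beyond the specified regimen as an overdose, reportable as an SAE. With two start days in the text, a site cannot tell whether ascorbate on C1D1 qualifies.

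**Working it through.** **1. Infusion rate**

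Inputs: volume 1000 mL (10.1.4, 7.6.2); cap 500 mL/h and rate 0.75–1 g/min (10.1.7); 75 kg example (Table 2, note 2).

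The protocol's example doses reproduce: 75 kg × 0.25, 0.5, 0.75 and 1 g/kg = 18.75, 37.5, 56.25 and 75 g.

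Formulas:
- time (min) = dose ÷ rate
- flow (mL/h) = 1000 ÷ time × 60
- shortest time under the cap = 1000 ÷ 500 h = 120 min
- mass rate at the cap = dose ÷ 120

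| Dose (75 kg) | Time at 1 to 0.75 g/min | Flow at 0.75 to 1 g/min | Mass rate at the cap |
|---|---|---|---|
| 18.75 g | 18.75–25 min | 2,400–3,200 mL/h | 0.156 g/min |
| 37.5 g | 37.5–50 min | 1,200–1,600 mL/h | 0.313 g/min |
| 56.25 g | 56.25–75 min | 800–1,067 mL/h | 0.469 g/min |
| 75 g | 75–100 min | 600–800 mL/h | 0.625 g/min |

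The full dose runs at 600/500 = 1.2 to 800/500 = 1.6 times the cap. The first titration dose runs at 4.8 to 6.4 times the cap.

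Both limits hold together only if dose ÷ 120 ≥ 0.75, that is, dose ≥ 90 g. At 90 g they meet at a single point (0.75 g/min, 500 mL/h). At the 100 g maximum they overlap from 0.75 to 0.833 g/min. A rate of 1 g/min always breaks the cap: even 100 g takes 100 min, which is 600 mL/h.

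The stated 90–120 minutes corresponds to 0.75–1 g/min for a 90 g dose (90/1 = 90; 90/0.75 = 120), not for the 75 g example (75–100 min). Ninety minutes is 1000/90 × 60 = 667 mL/h. Adding the 15-minute tolerance gives 105 minutes, still 571 mL/h.

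**2. Start day**

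Twice-weekly infusions with 3–4 day spacing (Table 2, note 4):

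| Start | Titration doses | First 1 g/kg | Infusions in cycle 1 (at full dose) |
|---|---|---|---|
| Day 1 | about D1, D4, D8 | about D11, week 2 | 4 weeks × 2 = 8 (8 − 3 = 5) |
| Day 8 | about D8, D11, D15 | about D18, week 3 | 3 weeks × 2 = 6 (6 − 3 = 3) |

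Only a day 1 start puts 1 g/kg in week 2, as the schema has it.

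**3. Renal impairment and CYP3A inhibitors**

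No arithmetic applies. At a creatinine clearance of, say, 40 mL/min, Section 8.2.2.2 gives no olaparib until recovery, Table 5 gives 200 mg twice daily, and the Renal Impairment subsection recommends that reduction and then allows discretion to change the dose or stop. For a CYP3A inhibitor with no alternative, Section 8.2.2.1 ends protocol treatment, whereas Section 7.7 and Table 6 continue it.

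**4. Effect on the design figures**

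None. With n = 12 and at least 2 responses, P(X ≥ 2) = 1 − (1−p)¹² − 12p(1−p)¹¹ gives 0.0486 at p = 0.03 and 0.801 at p = 0.23, in line with Section 13.5.

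**The case against.** The strongest reply concerns the start day. Two provisions written for cycle 1, Section 7.6.2 and the week 1 exception in the calendar footnote, agree on day 8. The grid's ascorbic acid row carries that footnote, and Table 2 describes a general cycle, so the specific text might be taken to govern. This does not settle it: the schema is also specific to cycle 1, and its titration and week 2 full dose fit only a day 1 start.

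On rate, the cap reads as a ceiling and appears twice, and note 3 to Table 2 allows adjustment. A site can obey the cap by infusing over 120 minutes. That is fair, but below 90 g the site then misses the stated mass rate, and the ± 15 minutes does not bring the 90-minute figure under the cap.

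On renal impairment, the later subsection only recommends reduction and then gives discretion, and a hold is not in itself removal from treatment. The second part stands. The discretion, however, adds a third instruction and leaves the first two in conflict.

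The CYP3A conflict arises only if an inhibitor becomes unavoidable on study, since these drugs are excluded at entry. That limits its frequency but does not resolve it.

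It also stands that the core regimen is consistent (olaparib 300 mg twice daily; target ascorbate 1 g/kg twice weekly, at least 24 hours apart), that the start-day gap is one week against a six-month assessment, and that the γH2AX work is exploratory. The effect on PSA50 has not been quantified.

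**Conclusion.** The concern holds: all four contradictions are in the current text. At the stated 1000 mL, the mass rate and the volume cap are incompatible for every dose below 90 g, which includes the 75 kg worked example and all its titration doses. The two start days move the first full dose by about a week and change cycle 1 from 8 infusions to 6. The renal and CYP3A instructions each lead to different actions for the same patient.

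The arithmetic assumes the 1000 mL volume and 3–4 day spacing given in the protocol. The size and operating characteristics of the design are unaffected; safety, uniform delivery across sites, drop-out and interpretation of the C1D8 sample are not. This must be fixed. No view is taken on which rate, start day or rule is right.

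**What to change.** Reconcile each conflict to one instruction, chosen by the clinical team, and carry it through the schema, Sections 7.1, 7.6, 7.7, 8.2.2, 10.1.4 and 10.1.7, and Tables 2, 5 and 6:

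- one ascorbate start day, with the calendar marks, footnote and week of full dose to match;
- one infusion limit compatible with the stated volume, doses (including titration doses) and infusion time;
- one action for moderate renal impairment;
- one action for an unavoidable CYP3A inhibitor, including whether re-escalation is allowed.

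Then label the C1D1 and C1D8 samples in Section 11.2 and the calendar to agree with the chosen start day. The cost is protocol amendment wording only; sample size and analysis do not change.

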## 10.1.8 Patient Care Implications

Too rapid intravenous administration of the solution may cause temporary faintness or dizziness. Expected adverse events and potential risks are described in **Section 7.9.** Appropriate dose modifications are described in **Section 8.2.** No investigational or commercial agents or therapies other than those described below may be administered with the intent to treat the patient's malignancy.

Diabetics, patients prone to recurrent renal calculi, those undergoing stool occult blood tests, and those on sodium-restricted diets or warfarin anticoagulant therapy should not take excessive doses of ascorbic acid over an extended period of time. Diabetics taking more than 500 mg of ascorbic acid daily may obtain false readings of their urinary glucose test. No exogenous ascorbic acid should be ingested for 48 to 72 hours before amine dependent stool occult blood tests are conducted because possible false-negative results may occur. Heparin, enoxaparin, aspirin, NSAIDS, or other anticoagulant therapies are allowed.

Ascorbic acid at pharmacologic doses can give false positive results for blood glucose with some commercial point of care glucometers (glucose meters), although this has not been seen with clinical chemistry laboratory autoanalyzers. Glucometers should not be used to measure blood glucose during and up to 10 hours after intravenous ascorbate administration. Patients should be counseled that correction of falsely high blood glucose levels with excess insulin may cause hypoglycemia and death, that some strips provide false readings while others, such as Bayer Contour are less likely to do so. They should also be counseled that if they do see high blood glucose readings following IV ascorbic acid, they should not increase their insulin unless the high glucose reading is confirmed at least 10 hours after IF AA administration.

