#### 7.2 Screening/Pretreatment Assessment (up to Day -28)

Before initiating any screening activities, the scope of the study should be explained to each patient. Patients should be advised of any known risks inherent to the planned procedures, any alternative treatment options, their right to withdraw from the study at any time for any reason, and their right to privacy. After this explanation, patients should be asked to sign and date a Notice of Privacy Practice research authorization/HIPAA form and an IRB-approved statement of informed consent that meets the requirements of the Code of Federal Regulations (Federal Register Vol. 46, No. 17, January 27, 1981, part 50).

The following assessments will be performed at the screening visit:

- Obtain informed consent and research authorization.
- Record demographics (including age) and medical history (including prior treatment for prostate carcinoma).
- Conduct physical exam (including vital signs, height/weight).
- Obtain history regarding prior treatment history for prostate cancer (including history of ADT, and history of radiation therapy or other local therapy).
- Obtain histologic/radiographic confirmation of disease. If radiographic studies have not been performed within 6 weeks prior to Cycle 1 Day 1, they must be obtained as part of screening.
- Perform laboratory tests: complete blood count w/diff, PSA, comprehensive metabolic panel, urinalysis, G6PD, testosterone.
- Baseline ECG
- Confirmation of 25% PSA rise on prior therapy.
- Determine suitability for olaparib and ascorbate therapy.
- Discuss concurrent medications.

Relevant information should be documented for registration and monitoring purposes. The institutional registration should be finalized, and appropriate documents faxed or emailed to the lead site/sponsor per **Section 6.0**.

Information for patients who do not meet the eligibility criteria to participate in this study (i.e. screening failures) should be captured in consortium database at the pretreatment assessment.

For any subject that has a DNA repair gene mutation identified during screening and is therefore not eligible for this trial will be referred to medical genetics for counseling and consideration of further targeted testing to determine if the identified mutation is present in the germline.

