# 7.3.1 Clinical, Laboratory, and Radiographic Assessments

Every week, patients will have a non-fasting blood drawn for the values listed below. Repeat labs are not needed on C1D1 as long as visit is within 7 days of screening visit blood draw.

CMP

**Note:** Patients with creatinine clearance between 51-100 mL/min either at trial enrolment or during the course of the trial should be monitored every week for laboratory assessment and toxicity evaluation.

On Day 1 of each cycle, patients will have a non-fasting blood drawn for the values listed below. Repeat labs are not needed on C1D1 as long as visit is within 7 days of screening visit blood draw.

- CBC
- PSA

Every 3 cycles, patients will have radiographic studies:

- CT chest, abdomen, and pelvis with contrast
- NM bone scan

Laboratory Safety Assessments

Full hematology assessments for safety (hemoglobin, red blood cells [RBC], platelets, mean cell volume [MCV], mean cell hemoglobin concentration [MCHC], mean cell hemoglobin [MCH], white blood cells [WBC], absolute differential white cell count (neutrophils, lymphocytes, monocytes, eosinophils and basophils) and absolute neutrophil count or segmented neutrophil count and Band forms should be performed at each Day 1 visit and when clinically indicated. If absolute differentials not available, please provide % differentials. Coagulation [activated partial thromboplastin time (APTT) and international normalized ratio (INR)] will be performed at baseline and if clinically indicated. Patients taking warfarin may not participate in this study.

Biochemistry assessments for safety (sodium, potassium, calcium, glucose, creatinine, total bilirubin, gamma glutamyl transferase [GGT], alkaline phosphatase [ALP], aspartate transaminase [AST], alanine transaminase [ALT], urea or blood urea nitrogen [BUN], total protein, albumin) should be performed at each Day 1, Day 8, Day 15, and Day 22 visit.

Urinalysis by dipstick should be performed at baseline and at subsequent timepoints only if clinically indicated. Microscopic analysis must be performed by the hospital's local laboratory if required.

Bone marrow or blood cytogenetic samples may be collected from patients with prolonged hematological toxicities as defined under **Section 8.2.2.3** *Dose Modifications for Toxicities.* 

Additional analyses may be performed if clinically indicated.

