# 7.9 Expected Adverse Events

# 7.9.1 Ascorbic Acid

Too rapid intravenous administration of the solution may cause temporary faintness or dizziness.

The most common side effects of ascorbic acid include: pain and swelling at administration sites, nausea, vomiting, diarrhea, dry mouth, loss of appetite, muscle weakness, dizziness, headache, phlebitis, hypertension, fatigue, and leakage of protein.

Less common side effects of ascorbic acid include: acute and chronic nephropathy, kidney stones, renal failure, hypernatremia, hypoalbuminemia, hyperglycemia, and hypokalemia.

Of note, it has been reported that patients with a history of glucose-6-phosphate dehydrogenase deficiency experienced hemolysis.

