# 8.0 DOSING DELAYS/MODIFICATIONS

# 8.1 Dosing Delays

All scheduled cycles occur over a 28-day period. If necessary, treatment may be delayed for up to 4 weeks. If treatment is delayed more than two weeks, the Principal Investigator must be contacted for further instructions on continued treatment. Additional delays or modifications to the treatment schedule must be approved by the Protocol Chair. When the delay is due to toxicity, then the next cycle may begin with a dose reduction.

Ascorbic acid will be withheld for the following drug-related toxicities:

- $Cr \ge 1.6 \times ULN$  (for patients with  $Cr \ge 1.6 \times ULN$ , calculated or measured creatinine clearance must be  $\ge 50 \text{ mL/minute}$  (Cockcroft-Gault))
- Common Terminology Criteria for Adverse Events (CTCAE) Grade 3 or 4 non-hematologic toxicity excluding asymptomatic electrolyte aberrations
- Any AE, laboratory abnormality, or intercurrent illness that, in the judgement of the investigator, warrants delaying the dose of study medication

Olaparib will be withheld for the following drug-related toxicities:

Absolute neutrophil count
 Platelets
 Hemoglobin
 Total bilirubin
 AST (SGOT)/ALT(SGPT)
 ≤ 750/ mm³, see Table 8
 ≤ 8 hgb, If < 10, see Table 7

 ≥ 1.5XULN
 ≥ 2.5 x ULN (<5x ULN if with known liver m

• AST (SGOT)/ALT(SGPT)  $\geq 2.5 \text{ x ULN (<}5\text{x ULN if with known liver metastases}$  provided bilirubin is normal)

- Common Terminology Criteria for Adverse Events (CTCAE) Grade 3 or 4 non-hematologic toxicity excluding asymptomatic electrolyte aberrations
- Any AE, laboratory abnormality, or intercurrent illness that, in the judgement of the investigator, warrants delaying the dose of study medication

If dosing parameters for Ascorbic Acid are not met, study participants may continue with olaparib therapy. If dosing parameters for olaparib or are not met, study participants may continue with Ascorbic Acid therapy. Dose interruptions are allowed as required, for a maximum of 4 weeks. Patients who require an interruption in olaparib or ascorbic acid for >4 weeks due to toxicity must permanently discontinue study drug unless an exemption is granted by the protocol chair (Refer to section 13.6 for stopping rule). Where toxicity reoccurs following re-challenge with study treatment, then the patient should be considered for dose reduction or must permanently discontinue study treatment per investigator judgement.

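### Section 10.1.8 cautions recurrent stone formers against prolonged excessive ascorbic acid, but no eligibility or participation rule applies this to open-ended dosing at 1 g/kg twice weekly

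*Combined protocol and SAP*

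**What the plan says.** Section 10.1.8 (Patient Care Implications, ascorbic acid) names five groups, "Diabetics, patients prone to recurrent renal calculi, those undergoing stool occult blood tests, and those on sodium-restricted diets or warfarin anticoagulant therapy", and states that they "should not take excessive doses of ascorbic acid over an extended period of time". It does not say what dose is excessive or whether the trial dose counts.

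Section 7.9.1 gives the less common effects of ascorbic acid as including "acute and chronic nephropathy, kidney stones, renal failure, hypernatremia". Section 4.2.8 names oxalic acid among its metabolites.

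Section 3.0 sets the dose at 1 g/kg twice weekly until objective progression, unacceptable toxicity or withdrawal. Section 7.10 calls 1 g/kg the maximum tolerated dose, capped at 100 g.

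The renal entry criterion (5.1 [11]) is creatinine up to 1.6 x ULN, with a clearance requirement above that. At screening, 7.2 has the site take a medical history and "Determine suitability for olaparib and ascorbate therapy". Section 7.3.1 adds: "Urinalysis by dipstick should be performed at baseline and at subsequent timepoints only if clinically indicated".

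**The concern.** The protocol warns that men prone to recurrent stones should avoid prolonged excessive ascorbic acid, and it lists stones and kidney injury as effects of the drug. It then gives that drug, with no fixed end, at what it calls the maximum tolerated dose, and never tells a site whether such a man may enter. Entry screening looks at kidney function, which does not reveal stone history.

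What is at stake is the safety of individual participants. Following 5.1 and 5.2 exactly can enrol a man whom the protocol's own caution describes. The analysis of PSA50 response is not affected.

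**Working it through.** **1. The plan's own dose figures.** Table 2, note 2, uses a 75 kg man. 75 x 0.25 = 18.75 g; 75 x 0.5 = 37.5 g; 75 x 0.75 = 56.25 g; 75 x 1 = 75 g. All four match the protocol.

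**2. Cumulative exposure.** Inputs: ascorbate starts on cycle 1 day 8 (7.6.2), so week 1 has none; two infusions per week; the first three doses are 0.25, 0.5 and 0.75 g/kg; later doses are 1 g/kg, or 0.75 g/kg if reduced (8.2.1). No missed doses are assumed.

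- Weekly at full dose: 2 x 75 = 150 g.
- Titration: 0.25 + 0.5 + 0.75 = 1.5 g/kg.
- Three cycles (to the first 12-week scan): 11 weeks x 2 = 22 infusions, 19 of them after titration. 1.5 + 19 x 1 = 20.5 g/kg; x 75 = 1,537.5 g. With all later doses reduced: 1.5 + 19 x 0.75 = 15.75 g/kg; x 75 = 1,181.25 g.
- Six cycles: 23 weeks x 2 = 46 infusions, 43 after titration. 1.5 + 43 x 1 = 44.5 g/kg; x 75 = 3,337.5 g. With all later doses reduced: 1.5 + 43 x 0.75 = 33.75 g/kg; x 75 = 2,531.25 g.

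For scale within the documents, 4.2.7 describes complementary-medicine use averaging 0.5 per kg (taken as g/kg; the unit is incomplete) for twenty doses, or 0.5 x 20 = 10 g/kg, and reports few adverse events in patients who were properly screened. The trial schedule reaches about twice that by 12 weeks (20.5 / 10 = 2.05). This does not show that the dose is excessive.

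**3. What each named group receives.**

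| Group in 10.1.8 | Specific instruction |
|---|---|
| Warfarin users | Barred from the trial (7.3.1, 7.7), for a stated interaction reason |
| Diabetics | Glucose-meter rule and insulin counselling (10.1.8) |
| Stool occult blood testing | No ascorbic acid for 48 to 72 hours before the test (10.1.8) |
| Recurrent stone formers | None found |
| Sodium-restricted diet | None found (see the other side of the case) |

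**4. A recurrent stone former with normal creatinine, taken through entry.**

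- 5.1 [11]: he meets the creatinine limit.
- 5.2 [1] to [23]: none names renal calculi. [18] covers a serious, uncontrolled disorder, which a history of stones need not be.
- 7.2: the history is taken, but the suitability step has no criteria.
- 6.2: the documents sent for central verification include laboratory results, scans and a note of prior therapies. Stone history is not listed.
- Baseline urinalysis and CT: required, but neither is tied to a stone-history rule.

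He passes every named criterion.

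**The case against.** The strongest reply is that the caution concerns excessive doses only and the protocol treats 1 g/kg as acceptable. Section 7.10 calls it the maximum tolerated dose, and 4.2.7 cites a dose-escalation study with no toxicity even above 1.5 g/kg. That stands against any claim of contradiction. Neither statement is about men prone to stones, however. If the sponsor regards the dose as acceptable for them, 10.1.8 should say so. The 500 mg daily figure in 10.1.8 does not settle it either: it concerns false urinary glucose readings and is no threshold for stones.

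A second reply is that silence in 5.2 does not mean admission. The warfarin bar also sits outside 5.2, eligibility is verified centrally (6.2), and it is monitored by the Protocol Chair or Coordinating Center (12.3). This stands in part. A reader might infer that each site decides alone, and that would be too strong. None of these checks names stones, though.

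A third reply points to safeguards on treatment: weekly chemistry, the creatinine and grade 3 or 4 holds in 8.1, the hold for "Any AE, laboratory abnormality, or intercurrent illness that, in the judgement of the investigator, warrants delaying the dose of study medication", CT every 12 weeks, resolution to grade 1 or baseline before restart (8.2), and a single permitted ascorbate reduction (8.2.1). These limit harm once something has been noticed. They do not screen for stone history.

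A reader might also extend the point to men on sodium-restricted diets and ask for a mandatory hold for asymptomatic hypernatremia, because 8.1 covers "Grade 3 or 4 non-hematologic toxicity excluding asymptomatic electrolyte aberrations". The documents do not adequately support this. They give no sodium content for the infusion, and the diluent is sterile water (10.1.4). The electrolyte exception applies to every patient and has nothing to do with diet. Sodium is in the regular panel ("Biochemistry assessments for safety (sodium, potassium, calcium, glucose, creatinine, total bilirubin"). Section 8.2.2.3, although under the olaparib heading, requires interruption for any grade 3 or 4 event judged related to study treatment, with no electrolyte exception.

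Finally, the documents do not prove that exclusion is the only possible remedy. That is fair; exclusion is a judgement about the simplest safe rule.

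**Conclusion.** The point holds for recurrent stone formers. The protocol states a caution, lists the matching harms, and has no rule that applies the caution to its own dose. A man with recurrent stones and normal creatinine is eligible under every named criterion, and only general judgement would keep him out.

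Its size can be given only as exposure: at 75 kg, about 1,181 to 1,538 g by 12 weeks and about 2,531 to 3,338 g by six cycles, depending on whether doses after titration are reduced. The documents give no stone rate and no count of affected men, so expected harm cannot be estimated.

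The conclusion rests on reading the 10.1.8 caution as relevant to prolonged dosing at the maximum tolerated dose. That is an inference, because excessive is undefined, so confidence is moderate. The change is worth making for participant safety; it does not bear on sample size, error rates or the primary analysis.

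**What to change.** Add one exclusion to 5.2: a history of recurrent renal calculi, with the threshold stated (for example, two or more episodes), checked from the medical history already taken under 7.2. Add one sentence to 10.1.8 saying that the stone-former part of the caution is applied through this exclusion at the trial dose.

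No new test or visit is needed. The cost is possibly a few fewer eligible men. Their number cannot be derived from the documents, and planned accrual is one patient per month (13.5), so each man excluded could lengthen enrolment slightly. No change is proposed for sodium-restricted diets or for the electrolyte wording in 8.1.
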